2.2 Background (CSF Sub-Study)

The central nervous system (CNS) is a frequent site of HIV replication [14] and HIV-induced neuronal injury leading to a spectrum of cognitive disorders, ranging from asymptomatic neuropsychological impairment to severe HIV-associated neurocognitive disorders (HAND) [15, 16]. While the incidence of HAND has declined in the potent antiretroviral (ARV) era, minor neurocognitive disorders (MND) remains a significant source of morbidity among treated HIV-individuals with a prevalence as high as 50% [17]. HIV neuropathology during ARV therapy may result from at least two interdependent mechanisms. First, persistent HIV replication in the CNS has been associated with neurocognitive syndromes in cross-sectional studies [3, 4] and predicts their future development in longitudinal studies [18]. Although ARV therapy reduces HIV replication in both the plasma and CSF in early-stage HIV disease, the rate of HIV decline in CSF is slower than in plasma among individuals with advanced HIV disease and may lead to on-going neuronal injury. Second, HIV infection of perivascular macrophages and microglia results in cellular activation of these cells. This inflammatory response within the CNS is thought to be an important mediator of indirect damage of uninfected neuronal cells leading to the neurodegeneration observed in HAND [19] and may persist even after HIV replication is suppressed [20].

In this sub-study we propose to evaluate the pharmacokinetics and therapeutic effects of MVC within the CNS among subjects with sub-optimal CD4 recovery despite plasma viral suppression. Paired plasma-CSF measures of MVC concentrations, HIV RNA and markers of immune activation will be obtained pre- and weeks 4 and 24 of MVC-treatment intensification.

2.2.1 Maraviroc

Maraviroc selectively binds to the human chemokine receptor CCR5 present on the cell membrane, preventing the interaction of HIV-1 gp120 and CCR5 necessary for CCR5-tropic HIV-1 to enter cells [21]. CXCR4-tropic and dual-tropic HIV-1 entry is not inhibited by MVC.

2.1.1.1 Safety and Tolerability

The safety profile of MVC is primarily based on 840 HIV-infected subjects who received at least one dose of MVC during two Phase 3 trials (MOTIVATE 1 and MOTIVATE 2) [22]. Treatment-experienced, triple-class drug resistant subjects with R5 tropic virus only and plasma viral loads above 5000 copies/mL were randomized in a 1:2:2 fashion to placebo, MVC once-daily or MVC twice-daily plus optimized background therapy (OBT) for 48 weeks. The most common adverse events reported with frequency rates higher than placebo, regardless of causality, were cough, pyrexia, upper respiratory tract infections, rash, musculoskeletal symptoms, abdominal pain and dizziness. Additional adverse events that occurred were diarrhea, edema, influenza, esophageal candidiasis, sleep disorders, rhinitis, parasomnias, and urinary abnormalities. In both studies, the rates of discontinuation due to adverse events were 4.9% in subjects receiving MVC twice daily + optimized background therapy (OBT) compared to 5.3% in those receiving OBT + placebo. Most of the adverse events reported were judged to be mild to moderate in severity.

Specific potential adverse events associated with MVC have been included in the package insert as a warning and precaution for use [23]. And these include:

Hepatotoxicity Events: One case of possible MVC-induced hepatotoxicity with allergic features has been reported in a study of healthy volunteers. Although an increase in hepatic adverse events was observed during studies of treatment-experienced subjects with HIV infection, there was no overall increase in ACTG Grade 3/4 liver function test abnormalities. In pooled analysis of A4001027 and A4001028 the percent of subjects experiencing grade 3/4 laboratory abnormalities (without regard to baseline values) receiving MVC (N=421) were similar to those that received placebo (N=207) in addition to OBT, including: AST 5xULN: 4.5% vs. 2.9%; ALT 5xULN: 2.4% vs. 3.4%; and Total Bili: 5.7% vs. 5.3%.

Cardiovascular Events: When MVC was administered to healthy volunteers at doses higher than the recommended dose, symptomatic postural hypotension was seen at a greater frequency than in placebo. At lower doses used in HIV subjects in Phase 3 studies, postural hypotension was seen at a rate similar to placebo (approximately 0.5%). However, eleven HIV subjects (1.3%) who received MVC had cardiovascular events including myocardial ischemia and/or infarction during the Phase 3 studies (total exposure 267 patient-years), while no subjects who received placebo had such events (total exposure 99 patient-years). These subjects generally had cardiac disease or cardiac risk

factors prior to MVC use, and the relative contribution of MV to these events is not known.

Potential Risk of Infection: Maraviroc antagonizes the CCR5 co-receptor located on some immune cells, and therefore could potentially increase the risk of developing infections. The overall incidence and severity of infection, as well as AIDS-defining category C infections, was comparable in the treatment groups during the Phase 3 studies. While there was a higher rate of certain upper respiratory tract infections reported in the MVC arm compared to placebo (20.0% versus 11.5%), there was a lower rate of pneumonia (2.1 % vs. 4.8%). In addition, a higher incidence of Herpes virus infections (11.4 per 100 patient-years) was also reported in the MVC arm when adjusted for exposure compared to placebo (8.2 per 100 patient-years).

Potential Risk of Malignancy: Blockade of the CCR5 inhibitor by MVC represents a theoretical risk for decreased immune surveillance and potential increased risk of malignancy. However, no increase in malignancy has been observed with MVC.

2.2.1.2 Drug Interactions and Special Populations

In vitro studies demonstrated that MVC is principally metabolized by the cytochrome P450 CYP3A and to a lesser extent CYP2C9. As a substrate of CYP3A and P-gp MVC pharmacokinetics are modulated by inhibitors and inducers of these enzymes/transporters and a dose adjustments are required when co-administered with those drugs (see section 5.4 Concomitant Medications).

Pregnancy: There are no adequate and well-controlled studies in pregnant women. The incidence of fetal variations and malformations was not increased in embryofetal toxicity studies in rats at exposures (AUC) approximately 20-fold higher and in rabbits at approximately 5-fold higher than human exposures at the recommended daily dose. Maraviroc is a Category B drug for pregnancy (see section 4.0 Selection and Enrollment of Subjects).

Renal Impairment: The safety and efficacy of MVC have not been specifically studied in patients with renal impairment. In the absence of metabolic inhibitors, renal clearance accounts for approximately 25% of total clearance of MVC. Patients with a creatinine clearance of less than 50 mL/min who receive MVC and a CYP3A inhibitor may be at an increased risk of adverse effects related to increased MVC concentrations, such as dizziness and postural hypotension; these subjects will be excluded (see section 4.0 Selection and Enrollment of Subjects).

Hepatic Impairment: The pharmacokinetics of MVC has not been sufficiently studied in patients with hepatic impairment. Because MVC is metabolized by the liver, concentrations are likely to be increased in these patients (see section 4.0 Selection and Enrollment of Subjects).

2.2.1.2 Impact on CD4 Recovery

There are no study results demonstrating the effect of MVC on clinical progression of HIV-1. However, the peripheral CD4 count is an accepted prognostic marker for HIV-related morbidity and mortality both among untreated and treated patients with viral suppression [24]. Interestingly, the use of CCR5 antagonists may increase CD4 recovery independent of their effect on viral replication.

The Merit study was a phase 3, prospective study of MVC in antiretroviral-naïve patients with R5 virus [25]. Subjects were randomized to either efavirenz (EFV) 600mg once daily (n=361) or MVC 300mg twice-daily (n=360) in combination zidovudine/ lamivudine for 48 weeks. Baseline characteristics were similar between the EFV and MVC treatment groups (median CD4: 254 vs. 241 cells/mL; median HIV RNA: 4.88 vs. 4.86 log₁₀ copies/mL). Despite a greater proportion of subjects in the EFV arm achieving viral suppression at 48 weeks (HIV RNA < 50 copies/mL: 69% vs. 64.4%), those receiving MVC experienced significantly greater CD4 recovery than the EFV group (mean CD4 gain: 169 vs. 142 cells/mm³).

The potential independent benefit in CD4 recovery with MVC has also been observed in treatment experienced patients with ongoing viral replication. Study A4001029 was prospective study in treatment-experienced with non-R5 tropic virus (i.e. X4, dual/mix or indeterminate) and plasma viral loads above 5000 copies/mL that were randomized to placebo, MVC once-daily or MRV twice-daily plus optimized background therapy (OBT) for 48 weeks [26]. In a planned interim analysis at week 24, a similar decrease in viral load was observed in all 3 treatment groups. However, even among subjects with dual or mixed tropic virus as baseline those receiving MVC twice-daily (N=52) had significantly greater CD4 recovery than the placebo arm (N=54) at week 24 (change in CD4: +62.4 vs. +35.7 cells/mL; P<0.05).

These results are consistent with a recent meta-analysis that evaluated difference in CD4 recovery during viral suppression among recent Phase 2 and Phase 3 HIV trials of new HIV agents [27]. This analysis included 37 treatment arms from 16 clinical trials, including the above mentioned trials and two additional trials with a different CCR5 inhibitor, vicriviroc. In analyses that adjusted for baseline HIV RNA and degree of viral suppression, the use of a CCR5 inhibitor was associated with a greater CD4 count increase (mean difference: +32 cells/mm³) after 24 weeks of treatment compared to non-CCR5-containing regimens. Together, these data suggest a favorable, independent effect of MVC on CD4 recovery during viral suppressive therapy with ART and that MVC is safe in subjects with CXCR4 or dual/mixed tropic HIV isolates.

2.3 Rationale (Main Study)

Blunted CD4⁺ T-cell responses during viral control may be a consequence of on-going T-cell destruction in the regenerative phase of CD4 recovery from activation-induced apoptosis [4, 28] and/or reduced production from decreased thymic output [29, 30]. Occult HIV replication may contribute to both processes. R5 HIV envelop glycoprotein (gp) 120 interacts with CCR5 receptors which induce a distinct gene expression profile of numerous activation and transcription factors, including; nuclear factor of activated T-cells (NFAT), NF- κ B and mitogen-activated protein kinase (MAPK)-related genes [31]. This receptor interaction by gp120 likely creates a replication permissive state in the cell and promotes viral replication from quiescent naïve T-cells with very low CCR5 expression. Further, R5 envelope protein engagement of CCR5 also induces caspase gene activity [31] and may consequently increase T-cell apoptosis rates of uninfected cells in the peripheral circulation as well as within the thymus itself.

[figure not shown]
CCR5 inhibitors can improve the clinical status of HIV-infected by two distinct mechanisms. First, by blocking HIV entry into CD4⁺ T-cells, CCR5 inhibitors have direct antiviral activity. Second, as the pro-inflammatory state of HIV infection up-regulates CCR5 ligands and receptors [32], these receptor antagonists may abrogate immune activation and resultant T-cell apoptosis. Importantly, MVC binds CCR5 receptors without inducing intracellular signaling or altering cell-surface expression [21]. Potentially, MVC intensification during viral suppression with ART may further decrease persistent activation-induced apoptosis and improve repair and remodeling of lymphoid tissue leading to increased CD4⁺ T-cell recovery and function.

It is well-recognized that the chemosensitivity and prognosis of some cancers is correlated with specific gene-expression profiles [33, 34], however, our understanding of host gene interactions with HIV during antiretroviral therapy and the impact on CD4⁺ T-cell recovery is at an early stage. Li et al. performed functional genomic analysis to identify treatment-responsive genes in HIV-infected patients initiating ART [35]. Genomic chip arrays were used to screen approximately 12,000 human genes of which ~ 200 genes' expression appeared to be modified in response to HIV therapy. Genes involved in T-cell apoptosis, immune activation and some chemokines and cognate receptors (i.e. CCR5, MIP-1 β , RANTES and others) were down-regulated, while genes involved in tissue repair and remodeling were up-regulated.

Based upon the biology of CCR5 and its role in HIV infection [36] and ART-responsive gene expression profiles observed by Li et al. [35], we have selected candidate genes involved in immune function whose expression may be further altered during CCR5 intensification. We hypothesize that expression will decrease among genes involved in immune activation (NF- κ B, MAPK, nuclear factor of activated T-cells, MYD88 and STAT1), apoptosis (Fas ligand and TRAIL) and trafficking/repopulation of T-cells (CCR5, MIP-1 α , MIP-1 β and RANTES) and increase among genes involved in tissue repair (platelet-derived growth factor,

insulin-like growth proteins and osteoblast-specific transcription factor) (**Figure 1**).

Figure 1. Model of gene expression due to anti-inflammatory affects of Maraviroc in combination with suppressive antiretroviral therapy

Chemokine receptors and their ligands are both redundant and pleiotropic in function and may have a varied spectrum of biologic activities in vivo which may not be represented by a small set of selected gene candidates. Further gene expression profiles of peripheral blood mononuclear cells differ from T-lymphocyte subsets [37]. Therefore, whole genome expression (38,000 genes) will initially be done on purified CD4+/CD8+ T-cells at baseline, week 4 and at week 24 of MVC intensification.

Use of MVC is indicated in combination with other antiretroviral agents for treatment-experienced adult patients infected with detectable CCR5-tropic HIV-1 virus and evidence of multi-drug resistant virus. The manufactures of MVC recommend that the following points should be considered when initiating therapy with MVC:

- Consider baseline tropism testing.
- Avoid in patients with dual/mixed or CXCR4-tropic HIV-1 as antiviral efficacy was not demonstrated in a phase 2 study of this patient group.
- The safety and efficacy have not been established in treatment-naïve adult patients or pediatric patients. [*although trials of MVC in naïve patients have shown comparable (though not strictly non-inferior) virologic efficacy to and EFV-containing regimen in this population*]

The current study proposes to use MVC for treatment-experienced patients with on-going viral suppression and without evidence of multi-drug resistant virus. Since the patients will have undetectable HIV RNA levels, baseline tropism

testing is not possible. The use of MVC in this patient population should be safe and offers potential therapeutic benefit for the following reasons:

First, in phase 3 studies, treatment failure on MVC was associated with detection of CXCR4-using (i.e., CXCR4- or dual/mixed-tropic) [23]. This CXCR4-using HIV virus could have appeared in two ways: 1. due to *de novo* mutations in viral envelope or 2. due to emergence of pre-existing, low frequency variants that were not detected on baseline tropism testing. In both scenarios, as consistent with development of drug resistance with other HIV medications, MVC-associated drug resistance emerged in the setting of on-going HIV replication (i.e. detectable plasma HIV loads). An important difference in the treatment population of this study is that subjects would have already initiated ARV therapy and achieved viral suppression for at least 12 months prior to study enrollment. In the setting of on-going viral suppression it is very unlikely that CXCR4 tropic virus will be selected during the 24 weeks of MVC treatment intensification.

Second, the clinical and laboratory safety and tolerance of MVC is comparable to standard therapy in both treatment-experienced [26] and treatment-naïve patients [25]. Among treatment-naïve patients, the rate of discontinuation due to adverse events was less in the MVC arm (4.2%) than among efavirenz-treated subjects (13.6%) [25].

Finally, suboptimal CD4+ T-cell recovery during ART is a common clinical dilemma and may affect as much as 40% of viral suppressed patients [4]. This suboptimal CD4+ T-cell response during therapy, or immunologic discordance, can have detrimental clinical consequences [38], including an increased rate of HIV associated infections, malignancies, and cardiovascular morbidity/mortality. In contrast, mortality rates for HIV-infected individuals during the era of potent HAART (2004 to 2006) have life expectancy rates comparable to matched HIV-negative controls within the first 5 years of seroconversion [39].

The aim of this study is to evaluate a potentially therapeutic immunomodulatory effect of MVC. Several measures of immune homeostasis will be determined in this study, including functional genomic analysis and extended T-cell phenotyping. Genes responsive to MVC therapy will be identified and categorized into functional groups. Based upon existing literature of the identified genes and observed immune responses (change in CD4/CD8 subsets) during MVC therapy, a model of CCR5 responsive-genes and potential impact on immune recovery will be outlined. Potentially, individuals experiencing immune discordance during suppressive ART may be better treated by MVC antiretroviral intensification.

2.3.1. Hypotheses

1. We hypothesize that expression will decrease among genes involved in immune activation (NF-kB, MAPK, nuclear factor of activated T-cells, MYD88 and STAT1), apoptosis (Fas ligand and TRAIL) and

trafficking/repopulation of T-cells (CCR5, MIP-1 α , MIP-1 β and RANTES) and increase among genes involved in tissue repair (platelet-derived growth factor, insulin-like growth proteins and osteoblast-specific transcription factor).

- a. The gene expression profiles induced by MVC will be associated with a favorable increase in the rate of CD4+ T-cell recovery.
- b. The rate of CD4 recovery (cells/month) will be greater during MVC compared to before.
- c. The proportion of cells expressing activation/ apoptosis markers will decrease from baseline and this decrease will be associated with improved CD4 recovery.
- d. The proportion of naïve cells will increase from baseline and this increase will be associated with improved CD4 recovery.
- e. The rate of CD4 recovery will be greater among those subjects receiving PI-containing treatment regimens compared to those receiving NNRTI-containing treatment regimen.

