9.4 Methods of Analysis

9.4.1 Analysis of Primary Objective

RNA from a set of 60 samples (30 at baseline and 30 at week 24) will be isolated, amplified, labeled and hybridized on the Sentrix Human-6 Expression BeadChip containing approximately 38,000 probes per chip. The Illumina platform will be used which is a one-color platform using cye 3. Initially, filtering and pre-processing methods will be performed on the 38,000 genes in order to eliminate genes that are poorly measured or that exhibit aberrant values.

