9.4.1.2 Statistical Analysis

We expect to eliminate approximately 2-3% of genes in through pre-processing and filtering. The data will be randomly divided into a separate training set and a test set. 20 Baseline and 20 Week 24 samples will be used for training. The remaining 10 baseline and 10 week 24 samples will be used for testing. Using criteria such as 2-fold differences in gene expression between the two measured time points within the group of patients and a false discovery rate (the percentage of genes that will be identified by chance) of less than 2%, Significance Analysis of Microarrays (SAM) [59]) will be applied to the training set to rank order genes that best can predict differences in gene expression profiles between the two time points. The SAM method identifies genes with statistically significant changes in expression by computing a score for each gene relative to the gene specific standard deviation. Genes with scores greater than a certain (adjustable) threshold will be declared significant.

The set of highest ranking genes identified with the SAM procedure will then be clustered using unsupervised hierarchical clustering analysis [60]. The purpose of this clustering analysis is to confirm the results from SAM and to further explore the microarray data in order to possibly reveal unknown subclasses. In unsupervised hierarchical clustering, no predefined reference vectors are used and the data is not partitioned into a particular cluster in a single step. Instead, a series of partitions takes place. Next, we will use methods such as prediction analysis of microarrays (PAM) based on nearest shrunken centroids [61] to devise a cross-validated gene expression predictor for these cluster-defined classes. The PAM method is a modification of the more standard nearest-centroid method. Each class centroid is shrunk toward the overall centroids after standardizing by the within-class standard deviation. The test set will then be used for validation of our

predictor. The genes that best predict the classes will be examined for similarities such as possibly participating in common genetic pathways.

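### Hypothesis 1 names 14 candidate genes or families with expected directions, but section 9.4 contains no test of them; a prespecified candidate and gene-set analysis should sit beside the genome-wide screen

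*Combined protocol and SAP*

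**What the plan says.** Section 2.3 (Rationale, Main Study) states that the candidates were chosen in advance: "we have selected candidate genes involved in immune function whose expression may be further altered during CCR5 intensification". Section 2.3.1 makes them Hypothesis 1, opening "We hypothesize that expression will decrease among genes involved in immune activation" and closing with the tissue-repair genes, the last of which are "insulin-like growth proteins and osteoblast-specific transcription factor". Each of the four groups has a stated direction.

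Section 2.3 also explains why the whole genome is measured: chemokine receptors and ligands have redundant and varied actions "which may not be represented by a small set of selected gene candidates".

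The primary analysis in 9.4.1 uses "RNA from a set of 60 samples (30 at baseline and 30 at week 24"). After pre-processing, 9.4.1.2 splits the data: "20 Baseline and 20 Week 24 samples will be used for training", and 10 of each are held out for testing. SAM ranks genes in the training set, with a 2-fold change and a false discovery rate (FDR) under 2% given as example criteria. Hierarchical clustering, a shrunken-centroid classifier (PAM) and test-set validation follow. The last step is: "The genes that best predict the classes will be examined for similarities such as possibly participating in common genetic pathways".

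**The concern.** A hypothesis that names genes and directions should come with a rule for judging it. Here the only route from the data to Hypothesis 1 is whether a named gene happens to appear on the list that SAM returns. This has two consequences.

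- **Absence is uninformative.** A gene can miss the list because of filtering, the FDR threshold set for 38,000 genes, the fold-change criterion, or the loss of a third of the patients to the test set. None of these is evidence that the gene did not move.
- **Presence has no decision rule.** The plan does not say how many of the 14 must appear, in which groups, or what to conclude if a group moves the opposite way.

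The choice of probes for names such as NF-kB or MAPK, and of which pathways to discuss, would then be made after the results are known.

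**Working it through.** **Step 1. Count the candidates (2.3.1).**
- Immune activation, expected down: 5
- Apoptosis, expected down: 2
- Trafficking and repopulation, expected down: 4
- Tissue repair, expected up: 3

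Total 5 + 2 + 4 + 3 = 14 names, 11 down and 3 up. Several are families, not single genes.

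**Step 2. Look for a test of them.**
- 9.4.1 and 9.4.1.2: filtering, SAM, clustering, PAM, validation, pathway inspection of the selected genes. No named gene, group or direction.
- 9.4.3.1, ten secondary items: item 3 compares gene lists by background regimen; item 4 tests cell-marker proportions, not expression. The general line on pre/post testing introduces these ten items and adds no candidate test.
- 2.3 also plans to sort genes into functional groups, but only genes already found responsive.

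Sub-hypotheses 1b and 1e have mixed models, and 1c and 1d have marker tests and a correlation. The gap is in the gene statement that heads Hypothesis 1.

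**Step 3. The plan's own power figure.** The first row of the table in 9.3 gives 77% (20 per group, biological variation 0.4, technical 0.3, signal-to-noise 3, Type 1 error 0.01, 2-fold change). A closed-form rank-sum approximation (efficiency 0.955, natural-log scale, signal-to-noise term left out) runs as follows:
- SD = √(0.4² + 0.3²) = 0.5; SE = 0.5 × √(2 / (20 × 0.955)) = 0.162; ln 2 / SE = 4.28
- two-sided 0.01: Φ(4.28 − 2.58) ≈ 96%
- 2% FDR with 500 of 38,000 changed (per-gene level about 0.0002): about 71%

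Neither gives 77%, and no variant tried reproduced all six rows. The figures come from an online calculator whose noise model is not given, so this is not evidence of an error. The point does not depend on the table.

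**Step 4. Illustrate the two thresholds.** Assume two-sided paired t-tests, one probe per name, the same 20 patients supplying both training samples, and change measured in SDs of the within-patient difference. SAM uses its own statistic, so this approximates it.

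Candidate test, 30 pairs:
- level = 0.05 / 14 = 0.0036 (the first and strictest Holm step)
- critical t on 29 df = 3.17
- 80% power (noncentral t) at a change of **0.74 SD**

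Planned screen, 20 pairs, 2% FDR, 500 of 38,000 changed, at 80% power:
- level = (0.02 / 0.98) × (500 × 0.8) / 37,500 = 0.00022
- critical t on 19 df = 4.55
- 80% power at a change of **1.24 SD**

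Sensitivity:
- if only 50 genes truly change, the screen's level is (0.02 / 0.98) × (50 × 0.8) / 37,950 = 0.00002 and it needs 1.49 SD
- if the names expand to 40 probes (an assumption), the candidate level is 0.05 / 40 = 0.00125 and the candidate test needs about 0.82 SD

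**Step 5. The fold-change criterion.** If a strict 2-fold cut is applied to the observed change, a gene whose true change is exactly 2-fold passes only about half the time, because the estimate falls on either side of the truth about equally often.

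**The case against.** The strongest defence is that the design is deliberate. The protocol says why it goes genome-wide, 9.1 calls the trial a pilot looking for associations, and objective 1.1.1 is to characterise changes; no objective asks for a candidate-gene test. SAM scores every gene that survives filtering, so the named genes can be looked up. Section 2.1 also flags proliferation, trafficking and activation genes for particular attention.

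Part of this stands. It justifies the screen, and it means that the trial will produce information bearing on Hypothesis 1. It does not supply a test: the directional hypothesis is restated in 2.3.1 after the reason for going genome-wide is given, and no rule turns the scores into a conclusion.

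Four stronger readings are tempting, and the documents do not support them.

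- *The screen has little power for any one gene.* A reader might back-solve an effect from the power table, taking 0.01 as a per-gene two-sided level, and then add the FDR penalty. Section 9.3 introduces the calculation through FDR control and enters 500 hits of 38,000, so the table may already allow for multiplicity. From the stated SDs, power for a 2-fold change at 20 per group and 2% FDR runs from about 49% (technical 0.4, natural log) to 99% (technical 0.3, log2).
- *The trial can say nothing about its first hypothesis.* Too strong, given the per-gene scores and planned functional grouping.
- *Figure 1 would be built from a post hoc list.* Figure 1 is cited with the directional hypothesis as the model held in advance. The model to be built from results is a separate goal in 2.1 and 2.3.
- *Week 4 can be added free.* Sections 2.3 and 3.5 plan week 4 arrays, but 9.4.1 lists only 60 samples at baseline and week 24.

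**Conclusion.** The concern holds as an omission that can be confirmed by reading: 14 genes or families in four groups have predicted directions, and section 9.4 tests no gene, group or direction among them. It is more than missing detail, because the samples already planned at baseline and week 24 allow a direct test.

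The gain in sensitivity is illustrative: about 0.74 SD against 1.24 SD at 80% power. It rests on paired t-tests, one probe per name, 500 truly changed genes, and use of all 30 patients. The real probe list will be longer than 14 and the candidate figure correspondingly higher. The text finding needs none of these assumptions.

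**What to change.** Add a prespecified candidate analysis to 9.4.1, alongside the screen:

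1. Fix the probe list for each of the four groups, including how families map to probes, before the arrays are read.
2. Test each listed probe by a paired baseline to week 24 comparison in all 30 patients, with Holm correction within the list.
3. Add one self-contained gene-set test for each group in its stated direction, and state the multiplicity rule across the four.
4. State that this analysis is separate from the training/test split and that its results do not feed the SAM/PAM predictor, so that the 10 held-out pairs remain a valid test set.
5. Include week 4 only if week 4 arrays are run, and reconcile 2.3 and 3.5 with the 60 samples in 9.4.1.
6. Keep the 38,000-gene screen, labelled as discovery.

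The cost is small: SAP wording, the work of fixing the list, the extra analysis, and a second set of gene-level tests to report next to the screen. The baseline to week 24 comparison needs no new arrays; a week 4 comparison might.
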